### 4.3 Sample Size Considerations

The primary endpoint in this power analysis is the Zarit's caregiving burden score. Assuming 20% attrition rate at the 6-month follow-up, we plan to initially enroll totally 240 family caregivers who will be equally randomized into two will be equally randomized into two arms (120 per arm), and we expect a minimum of 100 caregivers per arm to complete the 6-month assessment. The sample size of 100 in each arm can guarantee 80% power at significance level 0.05 to detect the effect size of 0.28 standard deviation (SD) difference between baseline and 6 months follow-up in a two-sided paired t-test. (See Table 4). Nicholas et al. reported the effect size of 0.33SD of Zarit's score from the REACH VA intervention (also between baseline and 6-month follow-up). While GP4C will use a different delivery strategy than used in the REACH II and REACH VA trials, core therapeutic materials and techniques of the intervention are maintained. Thus, we expect GP4C to have a similar impact on caregiver outcomes as observed in prior REACH II trial. Thus, we conclude that enrolling 120 caregivers per arm (100 available at 6 months) will achieve sufficient statistical power to detect the effectiveness of the proposed interventions, even if the GP4C full functionality intervention is slightly less robust than the original REACH interventions.

*Table 4. Sample size and power by effect size*

| Effect size of 0.28 standard deviation (SD) difference |       | Effect size of 0.33 standard deviation (SD) difference |       |
|--|-------|--|-------|
| Sample Size  | Power | Sample Size  | Power |
| 70   | .646  | 70   | .777  |
| 80   | .706  | 80   | .830  |
| 90   | .757  | 90   | .872  |
| 100  | .800  | 100  | .905  |
| 110  | .834  | 110  | .929  |
| 120  | .868  | 120  | .948  |
| 130  | .893  | 130  | .962  |
| 140  | .914  | 140  | .972  |
| 150  | .931  | 150  | .980  |

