## 5 Outcome Measures

### Change from Baseline Caregiving Burden at 6 months

A 12-item version of the Zarit Caregiver Burden Interview. The Zarit Caregiver Burden Interview (ZBI) is an assessment tool for evaluating caregiver burden. The ZBI consists of 12 items representing a statement related to some aspect of perceived burden. Respondents (i.e., caregivers) rate each item ranging 0 (=never) to 4 (=nearly always). Total ZBI score is the summation of 12 items ranging from 0 to 48. Higher scores indicate greater burden.

[Time Frame: Baseline and six months]

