## 6 Statistical Methods and Analyses

Caregiver participants will be randomized to the two intervention arms (GP4C and R4C) with the ratio of 1:1. Primary and secondary outcomes, including the Zarit's caregiving burden interview, will be assessed at baseline and 6-month follow-up. Covariates in the analysis include demographic characteristics of the caregivers. Common descriptive statistics (mean, standard deviation, median, interquartile range for continuous variable; frequency and percentage for categorical variables) will be calculated for all covariates in each intervention arm and the two arms will be compared at baseline. Goals of our statistical analysis will be to evaluate the effectiveness of each intervention arm and to compare the two arms. For each intervention arm, the difference between 6-month follow-up and baseline will be computed. Paired t-test and Wilcoxon signed-rank test will be used to detect significant changes in outcome variables at 6-month follow-up since the baseline. Medians, means, and 95% confidence intervals of the differences will be calculated using both empirical percentiles and normal approximation. Multiple comparison adjustments, e.g., Holm-Bonferroni method and Hochberg procedure, will be implemented to control the family wise error rate when testing multiple outcome measures in Section 5.

The two intervention arms will be compared at each follow-up time and for the whole trial period. We will compare the two arms at 6-month follow-up using the two-sample t-test and Wilcoxon rank sum test for each of the two outcomes. The Anderson-Darling test will be used to check the normality assumption at baseline and follow-up times for the two outcome variables. If normal assumption is significantly violated then only nonparametric estimates and tests (i.e., median, IQR, empirical confidence intervals, Wilcoxon signed-rank test, and Wilcoxon rank sum test) will be reported, and data transformation, such as log and square root transformations, will be considered to normalize the outcome variables for further model-based testing. A pre-post analysis will be conducted to model the outcomes at 6-month follow-up to test the intervention arm and covariates adjusting the baseline measurements. The two arms will also be compared incorporating observations from baseline and follow-up in longitudinal analysis of covariance (ANCOVA) models or linear mixed-effects models having the follow-up time and adjusting for covariates.

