Given the fact that participants will be randomized into the two arms, the outcome variables will likely be comparable between the two arms at baseline. As a result, the interaction effect between the treatment arm and follow-up time (while adjusting for covariates) will be tested in the longitudinal analysis to evaluate the difference between the two intervention arms because a significant interaction indicates the caregiver's outcome has followed significantly different trajectories in the follow-up period depending on the treatment arm. Missing values may be possible because 1) some caregivers may be lost to follow-up, and 2) some caregiving recipients can be deceased prior to the follow-up. Missing patterns will be inspected and multiple imputation methods, including regression imputation, propensity score imputation, and MCMC imputation will be considered based on the missing mechanism^19. All tests will be two-sided and a p-value less than or equal to 0.05 will be reported as statistically significant. Statistical Analysis Software will be used to conduct the proposed analysis.

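### No analysis is named to carry the GP4C versus R4C conclusion: the first tests listed ignore baseline, and so does the only between-arm test on the non-normality list

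*SAP*

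**What the plan says.** The trial compares two randomised arms, with assessments at baseline and 6 months. SAP Section 5 heads its burden outcome "Change from Baseline Caregiving Burden at 6 months" and words most of the other outcome headings the same way. The Aim 2 hypothesis is that GP4C caregivers improve more than R4C caregivers.

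SAP Section 6 and the protocol's Data Analysis section both begin the arm comparison with: "We will compare the two arms at 6-month follow-up using the two-sample t-test and Wilcoxon rank sum test". The preceding paragraph computes differences from baseline, but separately within each arm.

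Other between-arm analyses follow:

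- **Pre-post model** of the 6-month outcome on arm and covariates, adjusted for the baseline measurement: SAP only.
- **Longitudinal ANCOVA** (the SAP adds linear mixed models as an alternative) using baseline and follow-up: both documents.
- **Arm-by-time interaction test** within the longitudinal analysis: both documents.

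Neither document says which of these leads. If an Anderson-Darling test rejects normality, both restrict reporting to a listed set of nonparametric estimates and tests. The signed-rank test on that list uses baseline, but within arm. The rank-sum test is its only between-arm test. The same sentence adds that log or square-root transformation will be considered so that models can still be fitted.

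**The concern.** Each caregiver supplies a baseline score, and the unadjusted tests make no use of it. When baseline and 6-month scores are correlated, adjustment removes variance from the arm comparison and corrects chance baseline imbalance. The documents' remark that randomised arms should be comparable at baseline does not remove this gain, because adjustment improves precision even under perfect balance.

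Two gaps let the unadjusted result decide the trial. First, several p-values will address one question with no rule for which prevails if they disagree. Second, under non-normality the unadjusted rank-sum is the only between-arm test certain to be reported.

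There is little slack to absorb a loss. The plan's 80% power is for a "difference between baseline and 6 months follow-up in a two-sided paired t-test", which is a within-arm comparison. No power is given for GP4C against R4C.

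**Working it through.** **Inputs from the documents.** Two-sided 0.05 (SAP Section 6: "All tests will be two-sided and a p-value less than or equal to 0.05 will be reported as statistically significant"). 1:1 allocation (same section). 100 completers per arm and an effect of 0.28 SD, with 0.33 SD from the earlier REACH VA study (SAP Section 4.3). Enrolment is 120 per arm with 20% attrition; 120 × 0.8 = 96, so 96 is checked as well as the stated 100.

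**Assumptions.** The baseline-to-6-month correlation, rho, is not in the documents and is varied. The 0.28 SD is carried over as a between-arm difference in SDs of the 6-month score, although in the plan it is a within-arm effect. Power is at 0.05, before the SAP's multiplicity adjustment across outcomes.

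**1. The plan's own figure.** For a paired t-test the noncentrality is d√n = 0.28 × √100 = 2.80. The normal approximation gives Φ(2.80 − 1.96) = 0.800; the noncentral t gives 0.792. At 0.33 SD the noncentral t gives 0.905. All 18 entries of Table 4 reproduce within 2 points.

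**2. Between arms, 6-month scores only.** The noncentrality is d√(n/2) = 0.28 × √50 = 1.980, against a critical value of about 1.97. Power is 0.504 at any rho.

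**3. Between arms, adjusted for baseline.** The residual SD is multiplied by √(1 − rho²), so the noncentrality is 1.980 / √(1 − rho²).

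| rho | √(1 − rho²) | noncentrality | adjusted power | loss if unadjusted |
|---|---|---|---|---|
| 0.3 | 0.954 | 2.08 | 0.542 | 3.8 points |
| 0.4 | 0.917 | 2.16 | 0.575 | 7.1 points |
| 0.5 | 0.866 | 2.29 | 0.624 | 12.0 points |
| 0.6 | 0.800 | 2.47 | 0.692 | 18.8 points |
| 0.7 | 0.714 | 2.77 | 0.788 | 28.4 points |

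At rho 0.8 the loss is about 40 points. In precision, ignoring baseline is equivalent to losing a share rho² of participants: 25% at rho 0.5.

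**4. Sensitivity.** With 96 per arm: 0.488 unadjusted, against 0.606 (rho 0.5) and 0.771 (rho 0.7) adjusted. With 0.33 SD and 100 per arm, by normal approximation: 0.646 against 0.769 at rho 0.5, a loss of 12.3 points. If 0.28 is instead read in SDs of the change score, the losses at rho 0.3, 0.5 and 0.7 are 4.1, 12.0 and 23.9 points.

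**5. Change scores.** Their SD is √(2(1 − rho)) times the raw SD, which equals the raw SD at rho 0.5. By normal approximation (on which the raw comparison gives 0.508), power is 0.508 at rho 0.5 and 0.387 at rho 0.3. With one baseline and one follow-up, the usual arm-by-time interaction is this same contrast, so it does not substitute for baseline adjustment.

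**6. The fallback.** Simulations used 100 per arm and 3,000 replicates per setting. On 0–48 integer scores, rank-sum power was 49%; rank ANCOVA gave 59% (rho 0.5) and 74% (rho 0.7). On a skewed 0–30 scale, rank-sum gave 49% and 48%; rank ANCOVA gave 58% and 74%. Type I error was 4.5–5.4% for every method.

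**7. Will the fallback be used?** Self-rated health is a single item scored 0 to 4. In simulation Anderson-Darling rejected normality for such an item in 100% of samples at n = 100 and n = 200, even with a symmetric distribution. For assumed skewed or ceiling-bounded CES-D and social support scores, rejection at n = 200 was 95–100%. For a normal-shaped burden score it was about 10%, so burden may escape.

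**The case against.** The strongest reply is that the plan already uses baseline. The SAP's pre-post model is the right one, both documents have longitudinal analyses, and the simple tests stand beside these. That is correct. A reader might infer that the plan discards baseline altogether, and the documents do not support that. What remains is that nothing says which analysis decides.

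A reader might also infer that non-normality leaves no adjusted route. That too goes further than the text, since modelling after transformation is to be considered. In simulation on a skewed 0–30 log-normal scale, ANCOVA after a log transform had 61% and 78% power at rho 0.5 and 0.7, against 59% and 73% for rank ANCOVA (type I error 4.9–5.7%). Either is a sound fallback, although a log-normal shape favours the log. But considering a transformation is not a commitment, and no log or square root makes a five-category item normal.

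A third inference is that comparing 6-month levels fails to test the change outcome. Under randomisation the expected arm difference is the same for levels and for change, and the recommended model also has the 6-month score as its response. Validity is not at issue.

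Finally, the Section 5 headings might mean that change scores enter the two-sample tests. Raw 6-month scores are the likelier reading, but not a certain one. Change scores would not remove the problem, because at rho 0.5 they gain nothing and below it they lose power.

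**Conclusion.** The concern stands as a matter of precedence and specification. An unadjusted comparison is listed first, no between-arm analysis is designated primary, the protocol lacks the pre-post model, and the unadjusted rank-sum is the only between-arm test guaranteed under non-normality.

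If an unadjusted test carries the conclusion, power falls from 54%, 62% or 79% to about 50% at rho 0.3, 0.5 or 0.7, a loss of about 4 to 28 points. This rests on 100 per arm, a between-arm difference of 0.28 SD borrowed from a within-arm effect, and a correlation the documents do not give. A reader might fix on a single figure such as 12 points, but that is only the rho 0.5 case. If the adjusted model leads, there is no loss. The direction does not depend on rho, because adjustment gains precision at any nonzero correlation.

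**What to change.** Make the same changes in SAP Section 6 and the protocol's Data Analysis section:

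1. Name the baseline-adjusted pre-post model (6-month score on arm plus baseline score) as the primary between-arm analysis, reporting the adjusted mean difference and its 95% CI. This adds the model to the protocol.
2. State that if normality is rejected, the between-arm test is a baseline-adjusted one in place of the unadjusted rank-sum: either the pre-post model on a transformed scale or rank ANCOVA, chosen in advance for each outcome. For the five-category health item, a transform will not deliver normality.
3. Keep unadjusted 6-month means and medians by arm as description only, and give the longitudinal analyses a supporting role.

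The cost is a little more wording and a fallback slightly less familiar to readers than the rank-sum test. No new data, visits or participants are needed.

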### Change from Baseline Self-rated health at 6 months

#### Assessment of perception of general health status:

A single item of self-rated health assess caregiver's perception on his/her own health from 0 (=excellent) to 4 (=poor).

[Time Frame: Baseline and six months]

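### An Anderson-Darling test on raw scores decides which simple results are reported and may change the model scale; fix the baseline-adjusted difference in points instead

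*SAP*

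**What the plan says.** SAP Section 6 plans paired tests of change within each arm and two-sample tests of the arms at 6 months, in both t-test and Wilcoxon form. It then sets a condition on them: "The Anderson-Darling test will be used to check the normality assumption at baseline and follow-up times for the two outcome variables". The consequence follows: "If normal assumption is significantly violated then only nonparametric estimates and tests". The list of what is reported is closed: "i.e., median, IQR, empirical confidence intervals, Wilcoxon signed-rank test, and Wilcoxon rank sum test) will be reported". For the models, "data transformation, such as log and square root transformations, will be considered to normalize the outcome variables for further model-based testing".

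The protocol's Data Analysis section carries the same rule. The two outcomes are not named in either document, while SAP Section 5 lists eight change-from-baseline outcomes. No level is given for the normality test beyond the general statement "All tests will be two-sided and a p-value less than or equal to 0.05 will be reported as statistically significant". Nothing says which arm or time point triggers the switch, or how zeros and back-transformation are handled.

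After the rule, the SAP plans, without condition, a pre-post model of the 6-month score adjusted for baseline, and a longitudinal ANCOVA or mixed model. The protocol has the longitudinal ANCOVA but not the pre-post model.

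**The concern.** A preliminary test of distribution shape decides what the reader sees, and for most of the planned analyses it looks at the wrong quantity. The paired t-test concerns changes, and the models concern residuals; the rule examines raw scores. The 6-month two-sample t-test does concern raw scores, but with about 100 per arm it does not need them to be normal.

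The outcomes are bounded integer scores and one is a single five-level item, so a sensitive test will detect departures that do no harm. Three things are then at stake:

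- The means and t-tests for that outcome drop out, including the paired t-test behind the sample size.
- What the rule leaves in the simple comparisons has no baseline-adjusted between-arm estimate.
- Whether the models run on points, logs or square roots is settled after the data are seen, with no criterion.

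**Working it through.** **1. Inputs.** From the SAP: 240 enrolled, 120 per arm, 20% attrition, at least 100 per arm expected at 6 months, two-sided 0.05 (Sections 4.3 and 6). Score ranges from Section 5: burden 0-48, CES-D 0-30, health 0-4, social support 8-32, PSS 0-40, PAC 0-44. The documents give no means, SDs, or baseline/6-month correlation, so those below are assumptions. The Anderson-Darling test is taken at 5% (critical value 0.752, mean and SD estimated).

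**2. The plan's own figure.** Paired t-test power uses noncentrality d√n with n − 1 df. For n = 100 and d = 0.28, noncentrality is 0.28 × 10 = 2.80 and power is 0.792, against 0.800 in Table 4. For d = 0.33 it is 3.30 and power is 0.905, against 0.905. Every row agrees within 0.01. Table 4 is therefore the power of a mean-based test that the rule would leave unreported if burden failed.

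**3. The five-level item.** The item is described as "A single item of self-rated health", scored "own health from 0 (=excellent) to 4 (=poor". Over a grid of 23,746 response distributions at n = 100, the smallest Anderson-Darling statistic is 3.02, against 0.752; at n = 50 it is 1.50. No distribution on the grid passes. At n = 100 the minimum is 3.94 after square root and 3.87 after log(x + 1), so transformation does not cure it.

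**4. Sum scores.** Rejection per test, simulated as rounded scaled-beta scores:

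| Score (assumed mean, SD) | Skew | n = 100 | n = 200 |
|---|---|---|---|
| Burden (24, 8) | 0.0 | 12% | 29% |
| Burden (18, 9) | 0.35 | 50% | 89% |
| Burden (12, 8) | 0.78 | 98% | 100% |
| CES-D (15, 6) | 0.0 | 28% | 70% |
| CES-D (10, 6) | 0.50 | 90% | 100% |
| PSS (20, 6) | 0.0 | 13% | 30% |
| PSS (14, 7) | 0.41 | 55% | 94% |
| PAC (30, 9) | −0.58 | 93% | 100% |

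A beta-binomial model for CES-D-like scores gives 75% at n = 96 and 99% at n = 192, so the rates depend on the model as well as on skew. Even for exactly normal data, two independent checks per outcome trigger falsely with probability 1 − 0.95² = 9.8%, and four with 1 − 0.95⁴ = 18.5%.

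**5. Raw scores against changes.** At an assumed correlation of 0.6 and n = 100, raw scores are rejected in 98% of tests and changes in 25% for a CES-D-like score (mean 9, SD 6). For a burden-like score (mean 18, SD 9) the figures are 49% and 9%.

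**6. Is the discarded t-test unsafe?** No. At 100 per arm its simulated type I error is 5.1% for the five-level item and 4.6% for a skewed CES-D-like score.

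**7. Power.** Take 96 per arm (120 × 0.8), correlation 0.6, and a between-arm shift of 0.33 SD. The plan cites 0.33 SD as a change from baseline; it is used here only for illustration. For normal data:

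- 6-month t-test: noncentrality 0.33 × √(96/2) = 2.286; power 62%.
- 6-month rank-sum: 2.286 × √(3/π) = 2.234; power about 60%.
- Baseline-adjusted: 0.33/√(1 − 0.36) = 0.4125, times √48 = 2.858; power 81%.

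Simulated beta-binomial scores:

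| Score | t-test | Rank-sum | Baseline-adjusted |
|---|---|---|---|
| CES-D-like | 60% | 66% | 80% |
| Burden, mean 18 | 63% | 65% | 82% |
| Burden, mean 24 | 62% | 59% | 81% |

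**8. Transformation.** Burden, CES-D, health, PSS and PAC can all equal 0, where a plain log is undefined, and no offset is given. Square root is defined at 0. Neither transformation corrects left skew.

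**The case against.** The strongest reply is that the rule removes less than it seems to, and much of that stands.

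- A reader might infer that no planned test concerns raw scores. The two-sample t-test at 6 months does, and the normality sentence follows it directly. For that test the check is unnecessary at this size, not misdirected.
- A reader might infer that the models move to a log or square-root scale and that no difference in points would be reported. Transformation is only to be considered, and the SAP plans the pre-post and longitudinal models unconditionally. They give differences in points unless a transformation is adopted. The log-of-zero problem also depends on that option.
- A reader might infer that the switch to ranks costs power. It does not, to any extent that matters: step 7 shows 60-63% for the t-test and 59-66% for rank-sum. The gain to 80-82% comes from baseline adjustment, which the 6-month t-test lacks as well.
- A reader might infer that the rule must fire for the health item. That holds only if the item is one of the two outcomes tested, and the documents do not say.
- Multiple imputation is also only to be considered, and the planned models could be pooled, so no conflict with imputation is established.

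The reply does not rescue the switch itself. It still has unnamed outcomes, no stated trigger or model-scale criterion, and a paired t-test that disappears when it fires.

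**Conclusion.** The concern holds as a defect of pre-specification, and the rule should be changed. A preliminary test that mean comparisons do not need at about 100 per arm decides which simple results are reported, and it leaves the scale of the models open until after the data are seen.

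How often it fires depends on the data. It is certain for the 0-4 item if tested. It is above 85% at n = 100 for the simulated sum scores with absolute skew of about 0.5 or more under the scaled-beta model. It is only about 12-13% for near-symmetric burden or PSS scores at n = 100, and about 30% at n = 200. All sum-score rates rest on assumed means, SDs and distributional forms. The power figures also rest on an assumed correlation of 0.6 and an illustrative 0.33 SD shift.

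The documents do not support the stronger conclusion that adjusted effects in points are lost or that the rank tests weaken the trial.

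**What to change.** Delete the Anderson-Darling switch and the log/square-root step from SAP Section 6 and from the protocol's Data Analysis section. For every scale score, state that the between-arm result is the baseline-adjusted GP4C minus R4C difference in original points from the pre-post model, with a 95% CI from robust or bootstrap errors, whatever the distribution. Add that model to the protocol, which lacks it. Check residuals for description only. Keep the Wilcoxon tests as supporting analyses and, optionally, add an ordinal model for the health item.

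The cost is wording in two documents, with no new data. The small downside is that a mean difference describes a markedly skewed outcome less well; the supporting analyses cover that.

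### The arm-by-time test that the plan justifies by comparable baselines does not, as conventionally fitted, use that premise; the SAP's own pre-post ANCOVA does and should be named primary

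*SAP*

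**What the plan says.** SAP Section 6 states that the primary and secondary outcomes "will be assessed at baseline and 6-month follow-up", so there are two visits. On adjustment it says: "Covariates in the analysis include demographic characteristics of the caregivers".

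The reasoning for the longitudinal comparison is that, given randomisation, "the outcome variables will likely be comparable between the two arms at baseline". From this the SAP concludes that "the interaction effect between the treatment arm and follow-up time (while adjusting for covariates) will be tested in the longitudinal analysis", and it describes this test as the means of evaluating the difference between the arms. The Data Analysis section of the protocol carries the same argument.

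The model itself is described only as "longitudinal analysis of covariance (ANCOVA) models or linear mixed-effects models having the follow-up time and adjusting for covariates". Neither document says whether baseline means are held equal across arms, whether covariates interact with time, or what covariance structure is used.

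The SAP also plans a separate model: "A pre-post analysis will be conducted to model the outcomes at 6-month follow-up to test the intervention arm and covariates adjusting the baseline measurements". That is an ANCOVA on the baseline value. The protocol's Data Analysis section has no such model. Both documents also list a two-sample t-test and a rank sum test at 6 months. Neither names one between-arm analysis as primary.

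**The concern.** The premise and the test do not fit together. If randomisation makes the baseline means equal, the analysis gains by assuming so. An ordinary arm-by-time model instead estimates a separate baseline mean in each arm and subtracts it. That discards the information in the premise and lets a chance baseline difference pass into the estimate through regression to the mean. The announced covariate adjustment may also be empty, because demographics are constant within a caregiver and drop out of the change.

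At stake are the precision of the between-arm comparison, which is the Aim 2 hypothesis, and clarity about which result will be reported as the answer. The interaction is the one analysis that the SAP argues for, so an analyst could reasonably present it as the main result.

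**Working it through.** **Inputs.** Two visits, 1:1 allocation and demographic covariates (SAP Section 6); 120 per arm enrolled and 20% attrition (SAP 4.3), so 120 × 0.80 = 96 followed up per arm. The correlation r between baseline and 6-month scores is not given in either document; 0.4 to 0.8 is assumed. Score SD is set to 1 at both visits.

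**The plan's own figure.** Table 4 gives 80.0% power for 100 caregivers and 0.28 SD. A two-sided paired t-test gives 79.2% by the noncentral t and 79.96% by the normal approximation, so the figure reproduces. It is for a within-arm change and says nothing about the precision of the interaction test.

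**Step 1: what the interaction estimates.** The conventional model is

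Y = μ + α·arm + τ·time + δ·arm×time + γ·x + caregiver effect + error.

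Subtracting baseline from 6 months within a caregiver leaves

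change = τ + δ·arm + error difference.

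The terms μ, α and γ·x cancel. With complete pairs, the estimate of δ is the difference in mean change, with or without the covariates.

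In a simulated trial with r = 0.6 and complete data, the change-score t-test, the mixed model without covariates and the mixed model with covariates all gave −0.4853 (SE 0.1046). ANCOVA on the same data had SE 0.0948. Adding covariate-by-time terms did move the interaction estimate, to −0.4893.

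**Step 2: precision with complete data.** Variance per caregiver is 2(1 − r) for the change and 1 − r² after adjusting for baseline. The ratio is (1 − r²) / [2(1 − r)] = (1 + r)/2.

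| r | 2(1 − r) | 1 − r² | Ratio | Variance lower by | SE lower by |
|---|---|---|---|---|---|
| 0.4 | 1.20 | 0.84 | 0.70 | 30% | 16% |
| 0.5 | 1.00 | 0.75 | 0.75 | 25% | 13% |
| 0.6 | 0.80 | 0.64 | 0.80 | 20% | 11% |
| 0.7 | 0.60 | 0.51 | 0.85 | 15% | 8% |
| 0.8 | 0.40 | 0.36 | 0.90 | 10% | 5% |

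Simulated ratios were 0.71, 0.80 and 0.90 at r = 0.4, 0.6 and 0.8.

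**Step 3: precision with attrition.** Let n = 120 per arm have a baseline and m = 96 a follow-up, in a likelihood mixed model.

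- Free baseline means: variance of the arm contrast = 2[(1 − r²)/m + (1 − r)²/n].
- Common baseline mean, or ANCOVA in completers: 2(1 − r²)/m.

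At r = 0.4: 2[0.84/96 + 0.36/120] = 0.0235 against 2 × 0.84/96 = 0.0175, ratio 0.745, a reduction of about 25%. At r = 0.8: 2[0.36/96 + 0.04/120] = 0.00817 against 0.0075, ratio 0.918, a reduction of about 8%.

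The exact identity of Step 1 no longer holds here. In a simulated trial with r = 0.4 and about 20% missing follow-up, the change score gave −0.146 (SE 0.166), the mixed model −0.206 (SE 0.162), and the mixed model with covariates −0.244 (SE 0.162).

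**Step 4: illustration in power.** Take 100 per arm and treat 0.28 as a between-arm difference in raw-score SDs. This is an assumption, since the plan uses 0.28 for a within-arm change. Power for the interaction against ANCOVA is then 44% and 58% at r = 0.4, 60% and 70% at r = 0.6, and 88% and 91% at r = 0.8. If 0.28 is instead in SDs of the change, interaction power is 51% at every r.

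**The case against.** The strongest reply is that the SAP already contains the remedy. Its pre-post model regresses the 6-month outcome on arm, covariates and baseline. That delivers the smaller variance and lets the covariates act on the 6-month value. This stands: a reader might infer that the trial's analysis as a whole forfeits 10% to 30% of its precision, and the SAP does not support that.

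Second, no model equation is written. A reader might infer that the SAP's text specifies a change-score t-test, but a common baseline mean or covariate-by-time terms are not ruled out, and longitudinal ANCOVA is an ambiguous term. This also stands, so the point concerns the conventional fit. It does not remove the need to act, because the unstated choices decide whether the adjustment does anything.

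Third, a reader might infer that the covariate adjustment has no effect at all. That needs complete pairs. The plan expects 20% attrition, considers multiple imputation, and under the protocol's Measures and Outcomes does not assess burden at 6 months after a care recipient's death. The equivalence is therefore approximate in this trial.

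Fourth, this is a matter of efficiency. Under randomisation the interaction test is unbiased with correct type I error, so nothing here makes it invalid. At high r the gain is small.

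What the reply does not answer is that the SAP gives the pre-post ANCOVA no priority over the interaction test, and that the protocol omits it.

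**Conclusion.** The concern holds in a limited form. The arm-by-time test is justified by a premise that its conventional fit does not use. Compared with a baseline-adjusted or baseline-constrained analysis, it gives up about 10% to 30% on the variance scale (5% to 16% on the SE scale) with complete data, or about 8% to 25% of variance with 96 of 120 per arm followed up. These ranges rest on r between 0.8 and 0.4, which is assumed, on equal SDs at the two visits, and on a free arm main effect.

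The loss belongs to that one test. It matters because that is the test singled out to evaluate the arm difference, no primary between-arm analysis is named, and the protocol has no separate baseline-adjusted model to fall back on.

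**What to change.** In SAP Section 6, name the existing pre-post ANCOVA (6-month outcome on arm, baseline value and the covariates) as the primary between-arm analysis, and add it to the protocol's Data Analysis section.

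If the longitudinal model is kept, make it secondary and write it out:

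- a common baseline mean, with no arm main effect;
- a time effect;
- an arm-by-post-baseline term as the treatment effect, reported with its 95% CI;
- covariate-by-time terms, so that the covariates act on the 6-month value.

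The cost is a text edit in two documents. No new data, visits or participants are needed.
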